The upper age limit of < 12 years was chosen based on currently approved ages, ie, pediatric subjects who do not qualify for commercial product are eligible to participate in this study. The lower age limit was selected based on appearance of first HAE symptoms ([Bork, Meng et al. 2006](#), [Farkas 2010](#), [Christiansen, Davis et al. 2016](#)). Importantly, no other prophylactic therapy is approved for children from 2 to < 6 years of age. The only therapies approved for pediatric patients aged 6 to < 12 years are injectables, so having an oral prophylactic therapy available as an option for young children would represent a needed advancement in the treatment of HAE patients. While HAE attacks are rarer in young children, an increase in the number of attacks is often seen around the ages of 3 to 6 years and at puberty ([Farkas 2010](#)). Including children as young as 2 years old such that the label would include patients at that age allows for treatment to be available for young children at an age where the attack frequency and severity may increase. Of note, enrolling subjects from birth to < 2 years old is not feasible nor justifiable given that the earliest possible HAE diagnosis is at 1 year of age and patient recruitment difficulties due to the extremely low prevalence of HAE and HAE symptoms in this age group. Nevertheless, the therapeutic need is recognized for the targeted indication and therefore all other pediatric subsets (2 to < 12 years of age) will be included.

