7.4. End of Study Definition

The end of study will be defined as when the last subject completes the last protocol-scheduled visit or sponsor-defined last visit should study be terminated early.

Berotralstat will be provided in Part 3 through Study Week 144 or until another mechanism is available to provide drug to the subject (eg, market access, separate study) or the sponsor discontinues development of the product for the prevention of angioedema attacks in children < 12 years of age.

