9.6. End-of-Study (EOS) Follow-up Visit

Subjects who discontinue berotralstat either at the Week 144 visit or earlier will be required to attend a follow-up visit 3 weeks (21 ± 3 days) after study drug discontinuation. Subjects will be discontinued from the study at this visit. Subjects who discontinue the study but will continue to receive berotralstat via another mechanism will have end-of-study assessments performed at their last regularly scheduled visit. After Week 48, subjects who discontinue study drug but continue to receive berotralstat via another mechanism will be considered completers.

If an AE is ongoing at the EOS visit, additional clinic visit(s) or telephone contact(s) may be warranted (see Section 11.1.2.1).

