4.4. Part 3: Berotralstat Treatment

After Week 48, subjects may continue to receive open label berotralstat in Part 3 (Weeks 48 through 144; a total of 96 weeks). Visits in Part 3 will occur every 24 weeks: Weeks 72, 96, 120, and 144. Also, during Part 3, sites will contact the P/C at 12-week intervals between study visits (ie, at Weeks 60, 84, 108, and 132) to assess the subjects' overall wellbeing. The contact should be an arranged tele-contact; however, it may become an on-site visit if the investigator or P/C considers an in-person visit necessary for medical management of the subject. Berotralstat will be provided in Part 3 through Study Week 144 or until another mechanism is available to provide drug to the subject (eg, market access, separate study) or the sponsor discontinues development of the product for the prevention of angioedema attacks in children < 12 years of age.

Subjects who discontinue berotralstat at Week 144 or earlier will be required to attend an EOS follow-up visit 3 weeks after study drug discontinuation. Subjects who discontinue the study but will continue to receive berotralstat via another mechanism will have EOS assessments performed at their last regularly scheduled visit. After Week 48, subjects who discontinue study drug but continue to receive berotralstat via another mechanism will be considered study completers.

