6.5.3. Completer Populations

Week 12 and Week 48 completers will include subjects from the Safety Population and will be analyzed for effectiveness endpoints and are defined below.

- A Week 12 completer is defined as a subject who completes dosing through the Week 12 visit.
- A Week 48 completer is defined as a subject who completes dosing through the Week 48 visit.

These definitions ignore missed doses and treatment interruptions due to AEs.

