9.1. Disposition of Subjects

Subject disposition will be presented for all subjects. The number and percentage of subjects included in the ITT, completer, safety, and PK populations will be presented by cohort. The number and percentage of subjects who complete each study part as well as the entire study and those who discontinue from the study will be provided. The reasons for early discontinuation will be presented.

A consolidated standards of reporting trials (CONSORT) diagram will be created based on the summary tables for the study report.

These data will also be listed by cohort and subject.

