11.2. Exposure to Study Treatment and Treatment Compliance

The number of subjects exposed to study treatment and the number of subjects who discontinue treatment early will be presented on the disposition table. A summary of exposure to study treatment will also be presented. Listings of exposure to study treatment and of drug accountability will be provided by subject and treatment. Kaplan-Meier plots of duration of study

treatment (eg, time to discontinuation) will be provided. Subjects who discontinue study drug but continue to receive berotralstat via another mechanism will be considered completers.

Treatment compliance will be computed based on drug accountability by determining the number of capsules/packets taken relative to the number of capsules/packets that should have been administered.

For compliance (%) for the study period of interest based on the drug accountability page of the eCRF: *Number of Capsules or Packets Taken*

$$= \text{Number of Capsules or Packets Dispensed} - \text{Number of Capsules or Packets Returned} - \text{Number of Lost Capsules or Packets}$$

Expected Number of Tablets or Packets Taken

$$\begin{aligned} &= \sum_{i=1}^k (\text{CEILING}[\text{dose}_i \times (\text{Date of the Last Dose of Dose } i - \text{Date of the First Dose of Dose } i + 1)] - [\text{Interrupted}_i]) \\ &= (\text{CEILING}[\text{dose}_1 \times (\text{Date of the Last Dose of Dose } 1 - \text{Date of the First Dose of Dose } 1 + 1)] - [\text{Interrupted}_1]) \\ &\quad + \dots + (\text{CEILING}[\text{dose}_k \times (\text{Date of the Last Dose of Dose } k - \text{Date of the First Dose of Dose } k + 1)] - [\text{Interrupted}_k]) \end{aligned}$$

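### SAP 11.2 counts any child who moves to another berotralstat supply as a completer, without the after-Week-48 limit in Protocol 9.6 and SAP 4.4, and no censoring rule for these children is stated

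*SAP*

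**What the plan says.** Three places classify children who leave study drug but stay on berotralstat through another route.

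- SAP 11.2, in the paragraph that sends early treatment discontinuations to the disposition table and plans Kaplan-Meier plots of time to discontinuation: "Subjects who discontinue study drug but continue to receive berotralstat via another mechanism will be considered completers".
- SAP 4.4: "After Week 48, subjects who discontinue study drug but continue to receive berotralstat via another mechanism will be considered study completers".
- Protocol 9.6: "After Week 48, subjects who discontinue study drug but continue to receive berotralstat via another mechanism will be considered completers".

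SAP 6.5.3 sets a separate dosing-based definition: "A Week 48 completer is defined as a subject who completes dosing through the Week 48 visit".

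Early transfer is part of the design. Protocol 7.4 says: "Berotralstat will be provided in Part 3 through Study Week 144 or until another mechanism is available to provide drug to the subject". Market access and a separate study are its examples. According to SAP 4.4, children who leave the study for another supply "will have EOS assessments performed at their last regularly scheduled visit"; no later follow-up is described. SAP 9.1 then reports: "The number and percentage of subjects who complete each study part as well as the entire study". SAP 5.2 runs the disposition, dosing and safety summaries to Week 144.

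**The concern.** The SAP's completer rule conflicts with the protocol and with another section of the SAP, at the point where a programmer would look for it when building the discontinuation count and the persistence plot. A child who transfers before Week 48 is a completer under SAP 11.2, is not covered by the completer rule in SAP 4.4 or Protocol 9.6, and fails SAP 6.5.3.

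The SAP also does not say what being a completer means in a Kaplan-Meier plot. The child could be censored at the last study dose, carried event-free to Week 144, or handled in some other way. Two programmers could draw different curves from the same data.

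Even with the limit restored, completing the entire study covers both children seen at Week 144 and children who left soon after Week 48. The count alone does not tell a reader which is which.

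**Working it through.** **The plan's own figure.** The documents give no number for completion or transfer. The one design probability (Protocol 12.1, SAP 4.7) reproduces: 1 − 0.9^30 = 0.958, against a stated 96% or so. It does not depend on the completer rule.

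**The rules side by side, for three exit times.**

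| Child leaves for other supply | SAP 11.2 | SAP 4.4 and Protocol 9.6 | SAP 6.5.3, Week 48 set |
|---|---|---|---|
| Week 20 | Completer | Not covered by the rule | Not in the set |
| Soon after Week 48 | Completer | Completer | In the set |
| Week 60 | Completer | Completer | In the set |

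The conflict lies in the first row. In the other two rows the sections agree, and the question is what completion conveys:

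- Exit soon after Week 48: 48/144 = 33% of the planned berotralstat period.
- Exit at Week 60: 60/144 = 42%.

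**Who could reach age 12 on study.** Inputs: approval from 12 years (SAP 2, Protocol 4.1); entry below 12 years, which Protocol 4.4.3 links to market status ("pediatric subjects who do not qualify for commercial product are eligible to participate in this study"); a 12-week standard-of-care period before Day 1; Week 48 and Week 144 as the ends of Parts 2 and 3. Threshold age = 12 − weeks × 7/365.25.

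- Day 1 to Week 144: 144 × 7/365.25 = 2.76 years, so 9.24 years or more on Day 1.
- Day 1 to Week 48: 48 × 7/365.25 = 0.92 years, so 11.08 years or more on Day 1.
- Screening to Week 144 (156 weeks): 2.99 years, so 9.01 years or more at screening.
- Screening to Week 48 (60 weeks): 1.15 years, so 10.85 years or more at screening.

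**How many that might be.** The documents give no age distribution, so the following assumes uniform ages at screening and 30 children.

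| Assumed age range | Turn 12 by Week 144 | Of these, before Week 48 |
|---|---|---|
| 2 to < 12 | 30 × 2.99/10 = 9.0 | 30 × 1.15/10 = 3.4 |
| 4 to < 12 | 30 × 2.99/8 = 11.2 | 30 × 1.15/8 = 4.3 |
| 6 to < 12 | 30 × 2.99/6 = 14.9 | 30 × 1.15/6 = 5.7 |

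These are children who turn 12, not children who transfer. Protocol Table 1 describes the commercial capsule as approved for age 12 or more and weight 40 kg or more, which lowers the number for whom age alone opens access. In the other direction, a separate study, or a label extension supported by the interim analysis in SAP 5.1, could open supply to younger children during Part 3. The table is therefore neither an upper nor a lower bound on transfers.

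**Effect of one child on a percentage.** In a cohort at the minimum size of 4, reclassifying one child moves the completion figure by 1/4 = 25 points. Among 30 children it moves by 1/30 = 3.3 points.

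**The case against.** The strongest reply is that the after-Week-48 rule is a disclosed convention that follows the design: Part 3 supply ends at Week 144 or when another supply exists, so a child who transfers has reached one of two planned endpoints. That stands. No Week 144 completer population is defined.

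Shortened follow-up is also visible elsewhere. Duration of exposure in days is summarized by cohort (SAP 9.9), and Table 7 lists an exposure plot and an end-of-study listing at the final analysis. Continuous summaries carry the number with data (SAP 6.4), and vital signs are summarized by time point (SAP 11.6), so attendance at each Part 3 visit can be read off. A reader might infer that long-term safety is presented as resting on more children than were followed. The documents do not support that, because safety analyses use every dosed child and completer status enters no adverse-event or laboratory calculation.

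A reader might also infer that children past 9.24 years, or most of Cohort 1, will leave for commercial drug. Nothing requires a switch at 12, Table 1 adds the weight condition, access by country is not documented, and the remark in Protocol 4.4.3 on the median weight of 12-year-old girls is not an age distribution for Cohort 1.

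On the plot, it is fair to say that the likely intention is that transfers are not discontinuation events, and that censoring at last dose would be usual. But it is not written. Table shells are in a separate document (SAP 14.2), so a transfer row may exist there; the SAP text does not specify one.

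Finally, the pre-Week-48 conflict may be called theoretical, since the supply-ends-early clause concerns Part 3. That is only partly so: the end-of-study provision for transfers in Protocol 9.6 has no time limit, and a child of about 11.1 years or more on Day 1 turns 12 before Week 48.

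**Conclusion.** The inconsistency is real and narrow. SAP 11.2 lacks a limit that Protocol 9.6 and SAP 4.4 both impose, and read literally it changes how a transfer before Week 48 enters the early-discontinuation count and the persistence plot. Separately, completion of the entire study can mean as little as about one third of the 144 weeks, and the handling of transfers in the Kaplan-Meier plot is not stated.

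The number of children affected cannot be derived; the 9 to 15 of 30 in the illustration rests on assumed age distributions and counts birthdays, not exits. The consequence is confined to disposition and treatment-persistence displays. Primary PK, effectiveness (collected only to Week 48), adverse-event summaries and the Week 12 and Week 48 completer sets are unchanged. The documents do not support a claim that follow-up is concealed or that the safety conclusions are compromised.

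**What to change.** 1. In SAP 11.2, restore the words *After Week 48*, so that it agrees with Protocol 9.6 and SAP 4.4.
2. In SAP 9.1, specify a disposition row such as *transitioned to other berotralstat supply*, separate from *reached the Week 144 visit*.
3. In SAP 11.2, state that children who transfer are censored at their last study dose in the Kaplan-Meier plot, and print the numbers at risk at Weeks 48, 72, 96, 120 and 144. A footnote should say that these children wished to stay on berotralstat, so the censoring may not be independent of persistence.

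The cost is SAP wording, one table row and one at-risk line. Trial conduct and data collection do not change. The drawback for the sponsor is that the stated completion percentage may become less favourable.

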11.3. Clinical Laboratory Evaluations

Non-PK blood and urine samples will be obtained per the schedule of assessments in Table 2.

Laboratory test results and change from baseline will be summarized by panel, parameter, time point, and cohort. Laboratory results, including laboratory normal ranges, will be listed by cohort, subject, parameter, and time point.

11.3.1. Analysis of Abnormal Laboratory Values

Laboratory abnormalities will be graded according to the DAIDS (also see Section 6.7.6). Treatment-emergent graded toxicities are defined in Section 6.7.6 (including exceptions) and the number and percentage of subjects who experience treatment-emergent graded toxicities will be summarized by panel, parameter, time point, and cohort.

Laboratory toxicity shifts from baseline to worst post-baseline grade will be summarized by panel, parameter, toxicity grade, and cohort.

The following categories of abnormal hepatic laboratory values will be evaluated for any occurrence among all post baseline assessments (where “and” indicates elevations occurring at the same visit). Within each treatment group and laboratory parameter grouping, a subject may be counted once per elevation criteria using the worst-case result. That is, a subject with a worst-case alanine transaminase (ALT) elevation $>3 \times$ the ULN for a given treatment group would be counted once in the ALT $> 1.5 \times$ ULN category and once in the ALT $> 3 \times$ ULN

category, regardless of how many ALT elevations the subject had that met the $> 3 \times \text{ULN}$ and $> 1.5 \times \text{ULN}$ elevation criteria.

- ALT and/or aspartate transaminase (AST) $> 3 \times \text{ULN}$ and total bilirubin > 1.5 or $2 \times \text{ULN}$
- AST $> 1.5, 3, 5, 10,$ and $20 \times \text{ULN}$
- ALT $> 1.5, 3, 5, 10,$ and $20 \times \text{ULN}$
- Total bilirubin $> 1, 1.5,$ or $2 \times \text{ULN}$
- Alkaline phosphatase (ALP) $> 1.5 \times \text{ULN}$

Profiles of liver enzymes and bilirubin over time will be graphically displayed for subjects with any Grade 3 or 4 abnormality in these analytes. In addition, a listing of all liver function test (ALT, AST, bilirubin, ALP, gamma-glutamyl transferase) results for subjects experiencing a treatment-emergent Grade 3 or 4 liver function test will be provided.

In addition, a Hy's law plot, a shift plot showing liver safety panel tests over time (baseline vs. on-study), and distribution plots of ALT, AST, ALP, bilirubin, cholesterol, and triglycerides over time will be produced using the format recommended by the Food and Drug Administration (FDA)/Industry/Academia Safety Graphics working group (<https://www.ctspedia.org/do/view/CTSpedia/StatGraphHome>). Note that triglyceride data will be summarized separately for fasted and non-fasted values. The plots to be included are the scatter plot of maximum transaminase versus maximum bilirubin, the liver test safety panel over time and the distribution of ALT by time and treatment. The distribution plots for AST, ALP, bilirubin, cholesterol, and triglycerides will use the same format as is used for ALT.

